childbearing potential and who are sexually active are required to practice adequate methods of birth control. Female subjects for whom menopausal status is in doubt in the opinion of the investigator will be required to use an adequate form of birth control. Acceptable, adequate form of birth control is defined as consistent use of combined effective methods of contraception including at least 1 barrier method.

Male subjects who are sexually active will also be required to use an adequate form of birth control as described above.

8. Subject has the ability to comply with procedures for cognitive and other testing in the opinion of the investigator.
9. Subject must be able to ingest pills (in tablet form) whole.
10. Subject lives with (or has substantial periods of contact with) a regular caregiver who is willing to attend visits, oversee the subject's compliance with protocol-specified procedures and study medication, and report on subject's status, and who has substantial contact with the subject. If the caregiver does not cohabit with the subject, he/she ideally should have a minimum of 10 hours total and at least 3 days contact with the subject per week. Prior to randomization, study representatives will review eligibility of non-cohabitating caregivers. Every effort should be made to have the same caregiver throughout the study.
11. Subject has provided full written informed consent prior to the performance of any protocol-specified procedure; or if unable to provide informed consent due to cognitive status, subject has provided assent and a legally acceptable representative has provided full written informed consent on behalf of the subject.
12. Caregiver has provided full written informed consent on his/her own behalf prior to the performance of any protocol-specified procedure.
13. General health status is acceptable for participation in a 24-week study.

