8.1. Time and Events

The Time and Events Schedule ([Table 2](#)) displays each study assessment and procedure along with the time of occurrence. All study assessments should be conducted by the investigator, and/or a suitably qualified designee approved and documented for this study. All raters will be trained and certified to perform the specific rating scales in this study.

For Visit 2 there is a visit window of + 5 days. In the event the Single-Blind Run-In period is extended to repeat the MMSE, the new Visit 2 window will be + 3 days. For Visits 4 and 5 there is a visit window of ± 3 days; for all other post-randomization visits, there is a visit window of ± 5 days. It is important that all visits should be scheduled relative to the baseline visit, except for Visit 9 which should be scheduled relative to the last dose of IP. If the visit window is used, the subsequent visit should remain according to the planned visit schedule (i.e., the subsequent visit date should not be re-calculated from the date of the previous visit but should remain relative to baseline).

Information will be recorded in the source documents and, where appropriate, the eCRF.

Every effort should be made to administer the ADAS-Cog within ± 1 hour of the time of day of the baseline administration on subsequent visits for each subject due to the potential for circadian fluctuation in scores.

The order of rating scales should, when possible, be held constant, with the ADAS-Cog given to the subject first at each visit. The ADCS-ADL should be the first rating scale given to caregivers when possible at each visit.

If medical assessments are scheduled for the same nominal time, then the assessments should be given after the cognitive testing and occur in the following order whenever possible:

- 12-lead ECG
- Vital signs
- Blood draws

Screening Period (up to 28 days before Visit 2): Subjects will be screened for eligibility during the Screening Period. Subjects who do not qualify for the study during this period will be considered Screen Failures. An ICF will be signed by each subject, if he or she is able, or by the caregiver with subject assent. An ICF will also be signed by the caregiver before any study-specific procedures are performed. Subjects will be screened according to study inclusion/exclusion criteria. This Screening Period may be extended for up to an additional

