11.1.3. Informed Consent

The investigator is responsible for obtaining written informed consent from each individual participating in this study after adequate explanation of the aims, methods, objectives, and potential hazards of the study and before undertaking any study-related procedures. The investigator must utilize an IRB- or IEC-approved consent form for documenting written informed consent. Each informed consent will be appropriately signed and dated by the subject or the subject's legally authorized representative and the person obtaining consent. Consent from both the caregiver representative and subject will be obtained.

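### Section 8.1 lets the caregiver sign the subject's consent form, where inclusion criterion 11 and Section 11.1.3 require a legally recognized representative

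*Protocol*

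**What the plan says.** Four provisions of the protocol bear on consent for a subject who cannot give it.

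- **Section 8.1, Screening Period:** "An ICF will be signed by each subject, if he or she is able, or by the caregiver with subject assent". The next sentence adds: "An ICF will also be signed by the caregiver before any study-specific procedures are performed".
- **Section 6.2, criterion 11:** where cognitive status prevents the subject from consenting, "subject has provided assent and a legally acceptable representative has provided full written informed consent on behalf of the subject".
- **Section 6.2, criterion 12:** "Caregiver has provided full written informed consent on his/her own behalf prior to the performance of any protocol-specified procedure".
- **Section 11.1.3:** each consent is signed by the subject or by the subject's legally authorized representative, together with the person obtaining it. The section then adds: "Consent from both the caregiver representative and subject will be obtained".

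Criterion 10 in Section 6.2 says who the caregiver is: "Subject lives with (or has substantial periods of contact with) a regular caregiver who is willing to attend visits". That person must also oversee compliance and report on the subject's status. For a caregiver living elsewhere, the text continues: "If the caregiver does not cohabit with the subject, he/she ideally should have a minimum of 10 hours total", and at least 3 days of contact per week. Study representatives review such caregivers before randomization.

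**The concern.** Section 8.1 is the working instruction a site uses when the form is signed. For a subject who cannot sign, it names a different person from the one named in the eligibility criterion and in the investigator-responsibility section.

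The subjects at issue are those least able to protect their own interests. Every subject enters with a diagnosis of Alzheimer's disease and a Screening MMSE of 12 to 24, so the provision for subjects unable to consent may well be used. If the wrong person signs, the subject has been brought into the study without the consent that the protocol itself requires, and the site has a breach of criterion 11. The stake is subject protection and eligibility, not the statistical operating characteristics of the trial.

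**Working it through.** The plan gives no figure to reproduce and no formula applies. The check is a comparison of the texts.

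**Step 1: who signs the subject's form when the subject cannot?**

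| Provision | Signatory for the subject | Subject's part |
|---|---|---|
| Section 6.2, criterion 11 | Legally acceptable representative | Assent |
| Section 8.1 | Caregiver | Assent |
| Section 11.1.3, signature sentence | Legally authorized representative | Not stated |

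Criterion 11 and Section 11.1.3 agree in substance. Section 8.1 is the outlier.

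**Step 2: could the Section 8.1 sentence mean the caregiver's own consent?** No. The sentence that follows it provides for a further form signed by the caregiver, and its word *also* marks that form as additional. Criterion 12 separately covers the caregiver's consent for himself or herself. The disputed sentence therefore concerns the subject's form.

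**Step 3: is the caregiver necessarily the legal representative?** No. Criterion 10 sets requirements on regular contact, attendance, oversight and reporting. Cohabitation is not required, and the hours for a non-cohabiting caregiver are stated as an ideal. Neither that criterion nor any other text requires, or deems, the caregiver to hold legal authority. Equally, nothing prevents one person from holding both roles.

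**Step 4: when does the conflict arise?**

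- Subject able to consent: the subject signs and there is no conflict.
- Subject unable, caregiver is the legal representative: Section 8.1 and criterion 11 are both met.
- Subject unable, caregiver is not the legal representative: Section 8.1 is met, while criterion 11 and the signature rule of Section 11.1.3 are not.

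Only the third case is a failure.

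**Step 5: what can happen before the failure is noticed?** Criterion 11 places consent ahead of any protocol-specified procedure. Table 2 schedules the C-SSRS, urine drug screen, blood tests, ECG, neurological examination and MMSE at Screening, and MRI or CT if no recent scan exists. A caregiver's signature accepted under Section 8.1 would open the way to all of these.

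**Step 6: the last sentence of Section 11.1.3.** It uses a term, *caregiver representative*, that is not defined. It could mean the caregiver consenting under criterion 12, or a caregiver acting for the subject. It also refers to the subject's consent without repeating that a representative may give it.

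**The case against.** The strongest reply is that the protocol already contains the safeguard. The same paragraph of Section 8.1 has subjects screened against the inclusion and exclusion criteria. Only those who meet the screening criteria enter the run-in. Table 2 repeats the eligibility review at Baseline, Section 8 bars waivers except for immediate safety concerns, and Section 11.1.5 requires source records that document eligibility. A site applying all of this should notice that the representative's consent is missing. In addition, who counts as legally acceptable depends on national law, which Section 11.1.1 invokes and the documents do not set out, so in some places the caregiver may qualify.

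Much of this stands. It rules out saying that sites following Section 8.1 will, as a matter of course, enrol ineligible subjects. It does not remove the point. An eligibility check that catches the gap after Screening tests have begun can stop randomization, but it cannot supply consent for tests already done. The bar on waivers does not say which text governs, because it also makes adherence to Section 8 essential. With approximately 185 centers planned, uniform resolution of the discrepancy cannot be assumed.

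A reader might infer three stronger things that the documents do not support.

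- **That there are three competing rules.** The signature sentence in Section 11.1.3 matches criterion 11. Its closing sentence is loosely worded but can be read as the caregiver's consent plus the subject's consent, given personally or through a representative.
- **That the number affected can be calculated.** Table 4 puts 20% to 30% of about 1150 subjects at Baseline MMSE 10 to 15, which is 0.20 × 1150 = 230 to 0.30 × 1150 = 345. That is not a count of subjects lacking capacity. It is a Baseline stratum, whereas consent is taken at Screening, and the documents equate no MMSE score with incapacity. They also do not say how many caregivers lack legal authority.
- **That data would be lost, mainly from the lowest MMSE stratum.** Neither the ITT definition in Protocol Section 10.3.1 nor the one in SAP Section 4 excludes subjects for defective consent, and no provision in the documents says such data are removed.

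**Conclusion.** The inconsistency is real and current. Section 8.1 authorizes a signatory whom criterion 11 and Section 11.1.3 do not recognize unless that person also has legal standing. A site relying on that sentence could take consent from a caregiver without authority and start Screening procedures on a subject who does not meet criterion 11.

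The conclusion rests on two conditions holding together for a given subject: the subject cannot consent, and the signing caregiver is not the legally acceptable representative. How often both occur cannot be estimated from the documents. Sample size, power and alpha are unaffected. The point merits correction because a single such case is a failure of consent for a vulnerable subject, and because the correction is small.

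**What to change.** Two sentences should change.

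1. **Section 8.1, Screening Period.** Replace the caregiver alternative with: *or by a legally acceptable representative (who may be the caregiver if so authorized), with the subject's assent*. Keep the following sentence on the caregiver's own form as it is.
2. **Section 11.1.3, last sentence of the consent paragraph.** Replace it with wording such as: *The caregiver will consent to his or her own participation (criterion 12), and consent for the subject will be given by the subject or, with the subject's assent, by a legally acceptable representative (criterion 11)*. This removes the undefined term.

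Neither change adds a procedure, a visit or a form, because criteria 11 and 12 already require these consents. Subjects who cannot consent and have no available representative would be screened out, as criterion 11 already provides. No analysis text in the protocol or SAP needs to change.

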8.2. Critical Baseline Assessments

Those subjects whose MMSE at Baseline (Visit 3) has changed significantly (more than 3 points) from Screening (Visit 1) and/or those subjects whose MMSE at Baseline changes such that it falls outside the range 10-26 will not be randomized. The purpose of this is to exclude subjects whose baseline is so variable that any drug effect may not be clearly observable and also to exclude subjects whose baseline improves under placebo to the level of very mild, or whose baseline worsens to borderline severe, making effects of treatment intervention difficult to observe with the assessments included in this study. If a greater than 3-point difference between the Screening and Baseline MMSE score is in the setting of recent changes in AD medication, Single-Blind Run-In may be extended for an additional 3 weeks after discussion with the Medical Monitor, during which time MMSE stability defined as less than or equal to 3-point change over 3 weeks must be observed.

8.3. Study Assessments and Procedures

8.3.1. Efficacy Assessments

All study assessments should be conducted by the investigator, and/or a suitably qualified designee, all of whom will be trained and certified to administer these measures for this study. Every effort should be made for the same person to conduct specific assessments on each individual subject at each study visit. Assessments will be monitored for quality. Screening assessments along with accompanying data will be reviewed to insure that subjects meet the inclusion criteria. Other assessments will be monitored by using data collected. Additional information regarding the method of quality monitoring of efficacy assessments is provided in the Study Reference Manual.

8.3.1.1. Mini-Mental State Examination (MMSE)

The MMSE (Folstein et al, 1975) consists of 11 tests of orientation, memory (recent and immediate), concentration, language, and praxis. Scores range from 0 to 30, with lower scores indicating greater cognitive impairment. It is based on the performance of the subject and takes approximately 5 to 10 minutes to administer.

8.3.1.2. Alzheimer's Disease Assessment Scale – Cognitive Subscale (ADAS-Cog)

The 11-item and 13-item ADAS-Cog (Rosen et al, 1984; Mohs et al, 1997) assesses a range of cognitive abilities including memory, comprehension, orientation in time and place, and spontaneous speech. Most items are evaluated by tests, but some are dependent on clinician ratings on a 5-point scale. The ADAS-Cog-11 total score range is from 0 to 70, with a higher score indicating more severe cognitive impairment. The ADAS-Cog-13 is the ADAS-Cog-11 with 2 additional items: delayed word recall and total digit cancellation. Scores for the ADAS-Cog-13 range from 0 to 85 with higher scores indicating greater dysfunction. The scale takes approximately 30 to 40 minutes to administer. During the study visits where the ADAS-Cog is performed, the full ADAS-Cog-13 test items will be collected. The primary analysis will be of the ADAS-Cog-11 subset of tests from that battery and the full ADAS-Cog-13 will be analyzed as a secondary endpoint. When possible, the ADAS-Cog should always be the first assessment

conducted and should be administered, if possible, within ± 1 hour of the time of baseline administration at all subsequent visits to control for potential impact of circadian variation in performance.

8.3.1.3. Alzheimer's Disease Cooperative Study - Activities of Daily Living (ADCS-ADL)

The ADCS-ADL scale (Galasko et al, 1997) measures functional impairment in terms of activities of daily living. The ADCS-ADL is an interviewer-administered, informant-based scale where the informant (caregiver) responds to 23 activities of daily living questions about the subject. The questions range from basic to instrumental activities of daily living and take approximately 20 minutes to complete. The score ranges from 0 to 78; the lower the score, the greater the impairment.

8.3.1.4. Clinician's Interview-Based Impression of Change Plus Caregiver Interview (CIBIC+)

The CIBIC+ assessment (Schneider et al, 1997) measures the global functioning of the subject through structured interviews by an investigator with both the subject and caregiver. The CIBIS (Clinician's Interview-Based Impression of Severity) will be administered at Baseline and the CIBIC+ will be administered at subsequent study visits. The change from baseline is recorded on a 7-point scale with a score of 4 indicating no change, scores above 4 indicating worsening, and scores below 4 indicating improvement. This scale will be administered by a rater independent of the ADAS-Cog, who will be trained and certified for this study.

8.3.1.5. Neuropsychiatric Inventory (NPI)

The NPI (Cummings et al, 1994) is a behavior rating scale composed of a 12-item structured interview of the caregiver that is scored from 0 to 144 (the higher the score, the greater the psychiatric disturbance). It assesses 12 behavioral disturbances occurring in dementia patients: delusions, hallucinations, agitation, dysphoria, anxiety, apathy, irritability, euphoria, disinhibition, aberrant motor activity, night-time behavior disturbances, and eating disturbances. Both the frequency and the severity of each behavior are determined.

8.3.1.6. Resource Utilization in Dementia Lite (RUD Lite)

The RUD scale (Wimo et al, 1998) is designed to assess caregiver burden and provide pharmaco-economic data related to AD. The RUD Lite 3.3 includes both baseline and follow-up questions. Caregiver-related questions include a description of the caregiver for demographic information and time spent caring for the subject and changes in work status. Subject-related questions include residential status and healthcare resource utilization. In the event that a subject changes caregiver during the course of the study, the new caregiver must complete a baseline questionnaire at the earliest possible visit.

8.3.1.7. Dependence Scale

The DS measures the amount of assistance patients with dementia require in performing daily activities (Brickman et al, 2002). The caregiver answers questions about the dependency of the subject. The scale consists of 13 items, representing a range of severity from mild to severe levels of dependency. The score range is from 0 to 15 with higher scores indicating greater dependency.

8.3.1.8. EuroQol-5D

The EQ-5D is a standardized measure of health status that provides a measure of health-related quality of life that is widely used in clinical trials (Rabin and deCharro, 2001). For this study the EQ-5D will be a caregiver proxy assessment. The assessment will be completed by the caregiver and will assess the caregiver's impressions of how the subject would rate his/her own quality of life. The EQ-5D questionnaire consists of 2 components: the EQ-5D descriptive system and the EQ visual analogue scale (EQ-VAS). The EQ-5D descriptive system includes 5 dimensions: mobility, self-care, usual activities, pain/discomfort, and anxiety/depression. The EQ-VAS records overall health status on a 20-cm vertical line with a score of 0 (worst health one can imagine) to 100 (best health one can imagine).

8.3.2. Safety and Screening Assessments

8.3.2.1. Adverse Events

The investigator or site staff is responsible for detecting, documenting, and reporting events that meet the definition of an AE or SAE.

8.3.2.1.1. Definition of Adverse Events

An AE is any untoward medical occurrence associated with the use of a drug in humans, whether or not considered drug related. Therefore an AE can be ANY unfavorable and unintended sign (including an abnormal laboratory finding or vital sign measurement), symptom, or disease temporally associated with the use of a medicinal product, without any judgment about causality.

AEs are recorded from the time that informed consent is signed, including those that occur during the Single-Blind Run-in Period. Treatment emergent adverse events are defined as those that occur on or after the date of the first dose of double-blind investigational product.

Events meeting the definition of an AE **include**:

- Exacerbation of a chronic or intermittent pre-existing condition including either an increase in frequency and/or intensity of the condition.
- New conditions detected or diagnosed after investigational product administration even though it may have been present prior to the start of the study.
- Signs, symptoms, or the clinical sequelae of a suspected drug interaction.

- Signs, symptoms, or the clinical sequelae of a suspected overdose of either investigational product or a concomitant medication.
- Clinically significant abnormal findings (laboratory test results, vital signs, physical examination findings, ECGs, radiologic exams, or other studies) should be recorded as AEs. A “clinically significant” finding is one that affects clinical management, including additional visits, monitoring or referrals, diagnostic tests, or alteration of treatment, or that is considered clinically significant by the investigator. A clinically significant finding may be a change in a test that has previously been abnormal but now requires additional action.
- When a medical or surgical procedure is performed, the condition that leads to the procedure should be recorded as the AE.

Events that **do not** meet the definition of an AE include:

- Anticipated day-to-day fluctuations or expected progression of pre-existing disease(s) or condition(s) present or detected at the start of the study unless judged by investigator to be more severe than expected for the subject’s underlying condition.
- Abnormal laboratory, ECG, or vital sign measurements that are not labelled clinically significant (see definition above).
- Situations where an untoward medical occurrence did not occur (social and/or convenience admission to a hospital).
- Overdose in the absence of other AEs will not be reported as an AE in its own right.
- Changes in C-SSRS during the course of the study indicating worsening should be evaluated by the investigator for clinical significance, and if clinically significant (e.g., alteration in medical care or intervention is required), an associated AE should be recorded, if present. The AE should be the primary underlying clinical manifestation assessed as clinically significant, and not the change in score itself.

